The phase I portion of the trial will use the modified continual reassessment method (CRM) to determine the maximum tolerated dose (MTD). The primary endpoint for the phase II trial will be the disease-free survival rate (DFS) at one year, and a Simon two-stage design will be used to test the null hypothesis that the one-year DFS rate is 25% against the alternative that it is at least 40%. Adverse events will be monitored, and multiple regression, logistic regression, and Cox regression analyses will be performed to examine the association between GSTA1 enzymatic activity and busulfan metabolic rate, GSTA1 enzymatic activity and the incidence of toxicity, and pharmacogenomic predictors of DFS, respectively.

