Because delayed VOD (day 30 and day 60) of moderate severity has been observed in two of the 12 initial patients on study, the observation period for successive patients will be extended to 60 days before dose escalation. This will lead to accrual of a higher number of patients per dose level and therefore we anticipate up to 50 patients in the phase I trial.

Addendum June 2006: Pharmacokinetics for the initial 20 patients was performed in the cancer center core facility at UC. For logistical reasons and for more intensive monitoring another laboratory will be

used and technical modifications in sampling have been introduced. Therefore accrual will resume at dose level 0. This will result in accrual of an additional 20 patients to the protocol.

Phase II

The primary endpoint for the phase II portion of the trial is the disease-free survival rate (DFS) at one year defined as the proportion of patients alive and without evidence of recurrence one year after the initiation of therapy. All patients will be followed for a minimum of one year and we will test the null hypothesis that the DFS rate at twelve months is $\leq 25\%$ versus the alternative that it is at least 40%. A Simon (1989), optimal two-stage design will be employed in which 29 patients are enrolled in the first stage.⁶³ (Patients treated at the MT D during the phase I portion of the study will be included in the phase II trial.) If the number alive and without evidence of recurrence at twelve months is 7 or fewer, the study will be terminated for lack of efficacy. Otherwise, subject to the monitoring described below for graft failure, liver toxicity, and GVHD, an additional 43 patients will be enrolled for a total of 72. If 22 or fewer patients are disease free at 12 months the regimen will be rejected, whereas if 23 or more of the total 72 patients ($> 32\%$) are disease free, the regimen will be considered worthy of further evaluation in phase III trials. This design has an α -level of 10% and a power of 90% under the alternative hypothesis that the true 12-month DFS rate is 40%. The probability of early termination when the 12-month DFS rate is 25% is 0.56. However, to avoid a long suspension of the trial, accrual will continue into the second stage while the one-year outcomes in the 29 first stage patients are being accumulated.

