In addition, the incidence of graft failure, liver toxicity, and high-risk, extensive chronic GVHD at 18 months will be closely monitored and evaluated. For the primary endpoint of DFS, we will employ a Simon (1989) two-stage design. Graft failure, liver toxicity, and GVHD will be monitored at specified intervals as described below. An independent Data and Safety Monitoring Committee will be established to review the data and make recommendations regarding the continuation or discontinuation of the trial. This committee is organized by the University of Chicago Cancer Center (High risk protocol monitoring committee). Since the assumptions regarding efficacy and toxicity are the same, the related donor and unrelated donor subgroups will be combined for all analyses.

Adverse Event Monitoring

Graft failure and liver toxicity will be monitored and early termination of the trial will be considered if there is evidence that the graft failure rate is $> 10\%$ or the rate of liver toxicity is $> 15\%$. Specifically, for graft failure the data will be reviewed after successive cohorts of 10 patients have been treated and we will consider terminating the trial if 4 of the first 10, 6 of the first 20, 7 of 30, 9 of 40, 10 of 50, 12 of 60, or 13 of 70 have graft failure. For liver toxicity the trial will be stopped if 5 of the first 10, 7 of the first 20, 9 of 30, 11 of 40, 13 of 50, 15 of 60, or 17 of 70, develop liver toxicity. With regard to high-risk, extensive GVHD, we will review the data after the first 10, 20, and 30 patients with successful engraftment and without evidence of relapse reach their 18-month landmark. (By the time 30 patients have reached this point, all 72 patients will have almost surely been accrued.) Evidence that the rate of high-risk, extensive GVHD is $> 40\%$ will lead to consideration for early stopping. Specifically, if 8 of the first 10, 13 of the first 20, or 17 of 30 such patients develop GVHD at any time

prior to 18 months we will consider terminating the trial. Each of these three stopping guidelines approximates a Pocock (1977)⁶⁴ group sequential monitoring boundary for a one-sided, overall alpha level of 0.10.

Additional Statistical Analyses

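### The third GVHD look needs 30 patients, more than 72 enrolments are expected to yield at either design DFS rate, so it is more likely missed than held and the guideline loses power

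*Combined protocol and SAP*

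**What the plan says.** Section 14.0, Adverse Event Monitoring, schedules reviews of high-risk, extensive GVHD "after the first 10, 20, and 30 patients with successful engraftment and without evidence of relapse reach their 18-month landmark". Termination is considered if "8 of the first 10, 13 of the first 20, or 17 of 30 such patients develop GVHD at any time" before 18 months, the concern being a rate above 40%. The guideline is said to approximate a Pocock "group sequential monitoring boundary for a one-sided, overall alpha level of 0.10". A parenthesis adds: "By the time 30 patients have reached this point, all 72 patients will have almost surely been accrued".

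The supply of patients is set in the Phase II part of section 14.0. After 29 first-stage patients, "an additional 43 patients will be enrolled for a total of 72". The primary endpoint is "the proportion of patients alive and without evidence of recurrence one year after the initiation of therapy", and the Protocol Abstract says the design will "test the null hypothesis that the one-year DFS rate is 25% against the alternative that it is at least 40" per cent.

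No section compares 30 with the expected number of such patients, gives an 18-month DFS assumption, or states the power of the GVHD guideline.

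**The concern.** The looks count only patients who engraft, do not relapse and get to 18 months. The design's own DFS values limit how many there can be, and even at the 40% alternative the 12-month count averages 28.8, before any relapse or death between months 12 and 18. The parenthesis discusses when the 30-patient look falls and takes for granted that 30 will be reached.

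If the third look does not take place, the guideline works with one or two looks whose limits were set for three. Much of its ability to flag a high GVHD rate lies in the third look, and the loss is greatest when DFS is poor.

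**Working it through.** **Inputs.** Looks 10, 20, 30; limits 8, 13, 17; threshold rate 40%; one-sided alpha 0.10; N = 72; 12-month DFS 25% and 40% (all section 14.0). Three assumptions are mine:
- A patient who reaches the landmark is alive and relapse-free at 18 months.
- GVHD is independent of DFS.
- All 72 are enrolled and followed to 18 months.

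The loss of DFS from month 12 to month 18 is not given, so zero loss serves as the upper bound and other values are shown as a range.

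**1. The plan's own limits.** The one-sided Pocock constant for three looks at 0.10 is c = 1.6505. With a continuity correction, limit = ceil(0.4n + c·sqrt(0.24n) + 0.5):
- n = 10: 7.06, so 8
- n = 20: 12.12, so 13
- n = 30: 16.93, so 17

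These match. The Simon design also reproduces (alpha 0.098, power 0.901, early termination 0.557 at 25%).

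**2. Exact behaviour with all three looks.** Probability of first crossing at each look:

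| True GVHD rate | Look 1 | Look 2 | Look 3 | Total |
|---|---|---|---|---|
| 40% | 0.0123 | 0.0161 | 0.0319 | 0.060 |
| 60% | 0.1673 | 0.2710 | 0.2926 | 0.731 |

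At 60%, about 29 of the 73 percentage points come from the third look. The 60% rate is illustrative; the plan names no target.

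**3. Number reaching the landmark.** N18 ~ Binomial(72, d), where d is 18-month DFS:

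| d | Mean | P(N18 ≥ 20) | P(N18 ≥ 30) |
|---|---|---|---|
| 25% (null, no loss) | 18.0 | 0.33 | 0.0014 |
| 32% (40% with 20% relative loss) | 23.0 | 0.81 | 0.05 |
| 36% (40% with 10% relative loss) | 25.9 | 0.94 | 0.19 |
| 40% (alternative, no loss) | 28.8 | 0.99 | 0.43 |
| 45% | 32.4 | >0.99 | 0.75 |
| 50% | 36.0 | >0.99 | 0.94 |

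Under a constant hazard, 40% at 12 months becomes 0.40^1.5 = 25.3% at 18 months, and P(N18 ≥ 30) = 0.0017.

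**4. Realised stopping probability.** P(stop) = sum over looks of P(first crossing at look k) × P(N18 ≥ n_k). At a 60% GVHD rate:
- d = 40%: 0.1673×1.000 + 0.2710×0.9888 + 0.2926×0.4301 = 0.56
- d = 36%: 0.48
- d = 25%: 0.1673×0.9928 + 0.2710×0.3348 + 0.2926×0.0014 = 0.26

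At a 40% GVHD rate the same sum gives a false-stop probability of 0.042 at d = 40% and 0.018 at d = 25%.

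**5. An alternative set of looks.** Looks at 8, 16, 24 with limits 7, 10, 14 have exact alpha 0.0085 + 0.0523 + 0.0230 = 0.084 at a 40% GVHD rate. At 60% the first-crossing probabilities are 0.1064, 0.4254 and 0.1640 (total 0.70).
- d = 40%: P(N18 ≥ 16) > 0.99 and P(N18 ≥ 24) = 0.90, so P(stop) = 0.68
- d = 25%: 0.1064×0.9990 + 0.4254×0.7478 + 0.1640×0.0703 = 0.44
- d = 50%: 0.70, against 0.71 for the current looks

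**The case against.** Several points on the other side have force.

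- **The alternative is at least 40%, not exactly 40%.** At an 18-month DFS of 45% or 50% the third look takes place with probability 0.75 or 0.94. A reader might infer that it is fictitious under both hypotheses. That fits only the null; at exactly 40% the bound of 0.43 is not rare, and a much lower figure needs a late DFS loss that the documents do not state.
- **The second look is mostly safe.** A reader might infer that looks two and three will often both be missed. At DFS 40% with no late loss the second is held with probability 0.99.
- **The alpha statement is not breached.** The realised 0.018 to 0.042 might be read as a failure of the stated 0.10. But the exact value with all three looks is already 0.060, from discreteness and the continuity correction, and the text claims only an approximation. Only the fall below 0.060 comes from missed looks, and it is in the conservative direction.
- **The denominator is open.** Section 14.0 names engraftment and absence of relapse, not survival. If patients who die without relapse also count, DFS no longer bounds the yield: with 50% evaluable the chance of 30 is 0.94, and with 60% it exceeds 0.99.
- **The practical reach is limited.** Crossing a limit leads only to consideration of termination, with committee review, and section 17.0 adds regular toxicity reporting. The plan itself says the third look follows accrual. Near the null the regimen would usually be rejected on efficacy anyway.

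These points narrow the finding. They do not answer the mismatch between a final look of 30 and an expected yield of at most 18.0 or 28.8 under the alive-and-relapse-free reading.

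**Conclusion.** The concern holds in limited form. The final look size exceeds the expected yield at both design DFS values. The third look is practically out of reach at 25% and, at exactly 40%, more likely missed than held. At a 60% GVHD rate the guideline loses at least 17 percentage points of stopping probability at DFS 40% (0.73 to at most 0.56) and at least 47 at DFS 25% (0.73 to at most 0.26). The limits themselves are correctly derived for three looks.

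The result rests on the three assumptions listed with the inputs. The first matters most, and the wording favours it without settling it. Graft failures, a first-stage stop, or follow-up ending one year after accrual would lower the yield. In the last case about 15 patients (six months at 30 per year) would miss the landmark, and with 57 patients at 40% the chance of 30 is 0.036. That truncation is possible rather than certain, since the schedule of tests lists yearly follow-up to five years.

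This should be corrected, but it does not affect the primary endpoint.

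**What to change.** In section 14.0, Adverse Event Monitoring:

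1. Define the denominator: say whether a patient who dies without relapse before 18 months counts.
2. State the expected number of such patients at DFS 25% and 40%, with an assumed loss between months 12 and 18, and choose look sizes in that light.
3. Re-derive the limits by exact binomial calculation at an overall one-sided alpha of at most 0.10, and report the stopping probability at one or two higher GVHD rates. Looks at 8, 16 and 24 with limits 7, 10 and 14 are one example.
4. Keep the disclosure that the last look follows accrual, restated for the new final look size.

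This changes protocol wording only and needs no extra patients. It has four costs:
- Fewer patients stand behind each look.
- The false-stop rate moves nearer to the nominal 0.10 (0.084 against 0.060 with all looks), so part of the gain is paid for in alpha.
- Power is slightly lower than now if 18-month DFS is 50% or more (0.70 against 0.71).
- A look at 24 is still unlikely at the null (0.07), where the gain comes from the second look.

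Later looks would still mostly follow accrual. At DFS 40%, the 16th patient needs about 16/0.40 = 40 enrolments. With about 8 carried over from phase I and 30 per year, that is 32/30 + 1.5 = 2.6 years, while accrual ends at about 64/30 = 2.1 years.

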The use of a test-dose followed by frequent pharmacokinetic sampling will allow the assessment of individual patient pharmacokinetics and calculation of the dose necessary to achieve an intended AUC with subsequent doses.^{27,40} IV Busulfex has linear pharmacokinetics^{27,29,34,41} and does not accumulate even after repeated daily dosing. On the other hand, there continues to be considerable interpatient variability in pharmacokinetics and the AUC cannot reliably be predicted from the administered dose. On the other hand, there is considerable evidence to indicate that busulfan AUC is closely associated with toxicity and, AUC should guide dose escalation studies rather than administered dose.

In this study, all patients will receive an initial test dose of 0.5 mg/kg IV over 3 hours. Pharmacokinetic sampling will be performed at four time intervals after

completion of the infusion and used to calculate treatment doses necessary to achieve an intended AUC. The treatment doses will be administered as four daily doses. Pharmacokinetic sampling will be performed with the first and fourth dose to confirm the relationship between predicted and obtained AUC. The target starting daily AUC (4800 $\mu\text{mol}\cdot\text{min}$) is slightly lower than the median AUC (4897 $\mu\text{mol}\cdot\text{min}$) observed in the MD Anderson study with a fixed dose of 130 mg/kg .³⁵ One should however also take into account the additional one-time busulfan exposure (approximately 600 $\mu\text{mol}\cdot\text{min}$) from the test dose in our patients. Therefore, even at the starting target AUC, cumulative busulfan exposure for our patients at 19800 $\mu\text{mol}\cdot\text{min}$, should be slightly higher than the median exposure in the MD Anderson study of approximately 19600 $\mu\text{mol}\cdot\text{min}$.

Blood samples will be stored on each of the patients for subsequent pharmacogenomic studies. In patients with active AML and MDS tumor samples will be stored as well for subsequent pharmacogenomic studies.

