At least eight subtypes of soluble GST have been described, each with specific affinities and more or less tissue restricted expression. The pivotal GST for busulfan metabolism is GST A1.⁴⁴ GSTM1 accounts for approximately 48% of busulfan metabolism and a third GST, GSTP1 accounts for approximately 18%.^{45,46} GST A1 is expressed mainly in the liver, but can also be detected in the blood. In-vitro experiments indicate considerable inter-individual variation in hepatic expression of GST A1 which correlates closely with busulfan metabolizing potential.^{44,47} Surprisingly GSTA1 levels in the bloodstream as measured with a commercial kit also correlates with busulfan metabolizing activity and may represent a surrogate of GSTA1 activity in the liver.

SNP analysis demonstrates the existence of at least six polymorphic sites in the GSTA1 promoter, and the existence of five different alleles.^{44,48} Based on the relations between the haplotypes, two subclasses of GSTA1 can be distinguished, GSTA1A and GSTA1B with respectively two and three variants. According to Cole's, allelic variation in GSTA1 genotype accounts to a large extent for the highly variable activity of GSTA1. But the in-vivo relation between GSTA1 genotypes and busulfan pharmacokinetics, remains to be studied.

In vitro data suggest that sulfonated busulfan metabolites as well as GSH depletion contribute to toxicity of hepatocytes.⁴⁹ Others have shown that overexpression of GSTA1 in cell lines, results in protection against busulfan induced cell cycle arrest and induction of tissue factor expression, thus suggesting a potential link between GST A1 expression and busulfan induced toxicity.⁵⁰ It is therefore conceivable that differences in GSTA1 activity caused by GSTA1 polymorphisms affect busulfan toxicity independent of their postulated effects of busulfan pharmacokinetics.

GST-M1 is another hepatic GST that is responsible for a substantial proportion of busulfan metabolism. The GST M1 gene is known to be highly polymorphic with deletion of either or both genes at varying but significant frequencies in different ethnic groups. In a recent study of children with thalassemia receiving busulfan cyclophosphamide conditioning, GSTM1 null genotype was the most important risk factor for VOD.⁵¹

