Busulfan clearance was higher in patients with null genotype and first dose steady state concentration was lower. The mechanism by which GSTM1 null genotype causes increased risk for VOD is probably complex and may be related to direct toxicity of busulfan metabolites (perhaps due to reciprocal increased GSTA1 activity),⁵² intrahepatic GSH depletion or interaction of GSH depletion and cyclophosphamide toxicity. Confirmation of these results after conditioning with busulfan-fludarabine, is likely to provide important new information on this issue.

5.7 *Pharmacogenomic determinants of drug efficacy:*

In addition to studies relating GST polymorphism to toxicity, we will, in patients with leukemia, study leukemia blasts to determine the relation between polymorphisms relating to busulfan and/or fludarabine metabolism and efficacy. For this purpose, we will study a sample of leukemia cells obtained from the bone marrow. Such samples will be obtained from AML patients participating in the phase I and/or phase II portion of the protocol.

Although resistance to fludarabine may occur by several means, one proposed mechanism of cellular and clinical resistance is reduced intracellular drug accumulation⁵³. The early steps of plasma membrane transport, nucleoside phosphorylation, and nucleotide dephosphorylation determine intracellular accumulation of fludarabine and its metabolites. Fludarabine is administered as the 5'-nucleotide monophosphate and is converted to the nucleoside by the activity of serum phosphatase and ecto-5'nucleotidase (CD73). As fludarabine is a hydrophilic compound and does not readily cross plasma membranes by diffusion, the presence of functional nucleoside transporters that accept fludarabine as a permeant is required for cellular entry at rates sufficient to achieve cytotoxic levels of intracellular metabolites. Three human (h) nucleoside transporter proteins, equilibrative nucleoside transporter 1 (hENT1), equilibrative nucleoside transporter 2 (hENT2), and concentrative nucleoside transporter 3 (hCNT3), have been shown to mediate cellular entry of fludarabine⁵⁴⁻⁵⁶.

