9.1.3 Dose schedule (see also statistical plan)

The targeted daily AUC of busulfan will be determined using the modified continual reassessment method.

Target AUC's are the following:

Dose level 0: 4800 mcgr.min/L.dose

Dose level 1: 5800 mcgr.min/L.dose

Dose level 2: 6800 mcgr.min/L.dose

Dose level 3: 7800 mcgr.min/L.dose

Dose level 4: 8800 mcgr.min/L.dose

Dose level 5: 9800 mcgr.min/L.dose

We do not anticipate further dose-escalation beyond dose level 5. If such dose-escalation were to be considered, we would submit an amended protocol to the IRB.

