At the conclusion of the phase II trial, 90% confidence intervals will be generated for the DFS rate at 12 months, as well as for the incidence of graft failure, and the incidence of active and extensive GVHD. Kaplan-Meier (1958) estimates of disease-free and overall survival rates will be calculated,⁶⁵ and the median disease-free and overall survival times and their associated 90% confidence intervals derived using the method given in Brookmeyer and Crowley (1982).⁶⁶ Descriptive statistics related to the frequency of adverse events, including liver toxicity, and of changes in laboratory values will be generated. Association between GSTA1 enzymatic activity and busulfan metabolic rate (i.e. AUC, T_{1/2}) will be determined using the Pearson correlation coefficient or, in case of a monotone but non-linear relationship, by Spearman's rank correlation coefficient. To account for other determinants of metabolism, multiple linear regression analysis will also be performed. The relationship between enzymatic activity and incidence of VOD will be assessing using logistic regression analysis. Multiple logistic regression analysis may be attempted, depending on the frequency of VOD.

The relationship between GST polymorphisms and VOD will be analyzed using chi-square or Fisher's exact test. The association between polymorphisms and busulfan pharmacokinetics will be analyzed using a t-test or non-parametric Wilcoxon rank-sum test, as appropriate. Finally, the pharmacogenomic determinants of drug efficacy will be assess using Cox (1972) multivariable regression analysis⁶⁷ with time to disease progression or death as the outcome variable and genotype and busulfan pharmacokinetic parameters (AUC, etc.) as predictor variables.

Estimated duration of accrual

For the phase I trial, we estimate approximately 4-5 patients per month will be accrued, so that the target of 30 subjects should be reached in 6-7 months. For the phase II study, we expect to accrue about 30 such patients per year. Assuming about 6-10 patients from the phase I study participate, a little over two years of recruitment and one year of additional follow-up will be required to complete the phase II trial.

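### The only planned test of GST polymorphisms against VOD has no exposure term, so it cannot separate a direct genotype effect from one acting through achieved busulfan AUC (minor)

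*Combined protocol and SAP*

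**What the plan says.** Section 14.0 (Additional Statistical Analyses) gives one analysis of genotype against veno-occlusive disease: "The relationship between GST polymorphisms and VOD will be analyzed using chi-square" or Fisher's exact test. It names no stratification and no covariate.

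Other parts of the protocol bear on this:

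- Section 5.3.4 says that "busulfan AUC is closely associated with toxicity". It plans pharmacokinetic sampling at the first and fourth treatment doses; section 10.0 allows the third in place of the fourth.
- Section 5.6 calls it conceivable that GSTA1 differences "affect busulfan toxicity independent of their postulated effects of busulfan pharmacokinetics".
- Section 5.6 also cites a study of children with thalassemia in which GSTM1 null genotype was the main VOD risk factor, and reports: "Busulfan clearance was higher in patients with null genotype and first dose steady state concentration was lower". It wants this finding confirmed under busulfan-fludarabine.
- Section 9.1.3 lists targets from "Dose level 0: 4800 mcgr.min/L.dose" to "Dose level 5: 9800 mcgr.min/L.dose".
- For enzymatic activity against VOD, section 14.0 plans logistic regression, with a multivariable version that may be tried if VOD is frequent enough. That option follows the enzymatic-activity analysis and names no covariates.
- For efficacy, section 14.0 puts genotype and busulfan AUC into the same Cox model.

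**The concern.** A 2x2 table of genotype by VOD estimates the total effect: any direct effect plus whatever passes through exposure. If carriers reach a different AUC from non-carriers, the two parts add or cancel, and the table cannot say which. The cited GSTM1 pattern, with lower exposure but more VOD in null patients, is the cancelling case. There, a crude test could miss the association that the protocol hopes to confirm. In the adding case, a purely pharmacokinetic effect could be read as a direct one. The plan provides for exposure adjustment in efficacy but gives the polymorphism-VOD analysis no route to it.

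**Working it through.** **The plan's own figures.** No sample size, effect size, significance level or power is stated for this test. Nearby figures reproduce. Cumulative exposure at level 0 is 4 x 4800 + 600 = 19800, as in section 5.3.4. The Simon design (7/29, 22/72) gives early termination 0.557 at a DFS rate of 25% (stated 0.56), type I error 0.098 (stated 10%) and power 0.901 (stated 90%). The point does not depend on them.

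**Does the target range confound?** Level 5 is 9800/4800 = 2.04 times level 0. The CRM assigns levels from earlier DLT outcomes (section 14.0, Phase I), without regard to genotype, so target level and genotype are independent by design. The range adds variation in VOD risk but no bias.

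**Patients and events.** Phase I is 30 patients, or up to 50 plus the 20 of the June 2006 addendum if these add. Phase II is 72, including 6-10 from phase I (8 used).

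- Low: 30 + 72 - 8 = 94. High: 50 + 20 + 72 - 8 = 134.
- Assumed VOD rate 15% to 16.7%; the upper value is the 2 of 12 early patients with delayed moderate VOD.
- Events: 0.15 x 94 = 14.1 to 0.167 x 134 = 22.3.

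**Simulation** (2000 trials per setting, two-sided 0.05):

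- AUC = (4800 + 1000 x level) x exp(N(0, 0.15)) x (1 + shift x genotype)
- logit P(VOD) = logit(base) + log(OR_AUC) x (AUC - 6800)/1000 + log(OR_G) x genotype

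Assumptions not in the documents: genotype prevalence 50%; OR_AUC 1.5 or 2.0; base 15% when OR_G = 1 and 8% when OR_G = 4; phase I spread evenly over levels 0-4; the other 64 patients at level 2. Fisher's test is compared with a likelihood-ratio test of genotype given achieved AUC. Ranges cover both sample sizes and both OR_AUC values.

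| True OR_G | Shift in achieved AUC | Fisher rejects | AUC-adjusted rejects |
|---|---|---|---|
| 1 | 0 | 0.03-0.04 | about 0.05 |
| 1 | +10% | 0.06-0.13 | 0.05-0.06 |
| 1 | +20% | 0.16-0.50 | 0.05-0.065 |
| 1 | +30% | 0.36-0.87 | 0.05-0.065 |
| 4 | 0 | 0.54-0.77 | 0.67-0.83 |
| 4 | -20% | 0.04-0.27 | 0.44-0.63 |

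In the last row the median crude odds ratio is 1.3-2.1, against a true 4.

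**Is it only Fisher's conservatism?** With no shift, mostly yes. In a second model (110 patients, OR_G 3, OR_AUC 1.6-2.0), adjustment gains only about 2-5 percentage points of power over uncorrected chi-square. For example, at OR_AUC 1.6 with the main group at level 1, power is 0.36 for Fisher, 0.44 for chi-square and 0.46 adjusted. With a shift, no. At 10-20% lower AUC, chi-square power is 0.07-0.26 against 0.29-0.54 adjusted. At 10-20% higher AUC with no direct effect, chi-square rejects in 0.06-0.45 against 0.05-0.07.

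**Would target level serve as the covariate?** No. Target level is unrelated to genotype, so conditioning on it leaves the genotype-to-achieved-AUC path open. The covariate has to be achieved AUC.

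**The case against.** The best defence is that the plan does what its objective asks. Section 1 (objective 4.3) seeks potential determinants of toxicity, and a crude association serves that. The independence idea in section 5.6 is only a conjecture about GSTA1. Dosing to a target AUC is meant to weaken any genotype-exposure link, and section 14.0 separately tests polymorphisms against pharmacokinetics, so a link might be seen. The 10-30% shifts are assumed. The analysis has no decision rule.

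Most of this stands. It is why the crude test should stay and the point is minor. The separate pharmacokinetic test does not close the gap, however: two marginal tests do not yield a genotype effect at a given exposure, and a non-significant AUC difference does not exclude a shift large enough to matter.

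A reader might also infer more than the documents support:

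- *That the twofold target range confounds the test.* It does not, for the reason shown above. Moreover, 9800 is a ceiling that may not be reached, and phase II clusters at the MTD.
- *That the trial cannot answer the question.* Achieved AUC is collected. Only the specified test falls short.
- *That ancestry confounds the result.* Section 5.6 says that GSTM1 deletion occurs "at varying but significant frequencies in different ethnic groups", but nothing in the documents links ethnic group to VOD risk or shows that ethnic group is recorded. An ethnic stratum is not justified.

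**Conclusion.** The point holds in a limited form. The specified test measures total association and cannot address an effect independent of pharmacokinetics, although the data to do so are planned. If achieved AUC does not differ by genotype, the loss is a few points of power. If it differs by 10-20%, the crude test can miss a real direct effect or report one that runs wholly through exposure. Whether it will differ after AUC targeting is unknown. The cited GSTM1 data make it possible, and the documents give no size. All simulated figures rest on the assumptions listed. The MTD, DFS and safety-monitoring analyses are untouched. Severity: minor.

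**What to change.** Keep the chi-square or Fisher test, labelled as the total association, and add to section 14.0:

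> To examine an effect of genotype on VOD independent of pharmacokinetics, VOD will be modelled by penalised (Firth) logistic regression on genotype, with mean achieved treatment-dose AUC as a covariate and a term for the pharmacokinetic laboratory.

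The laboratory term is needed because the June 2006 addendum moves the assay to another laboratory, with changed sampling, after the initial 20 patients. State beforehand how the two sampled doses are averaged. Do not substitute target level for achieved AUC, and do not add an ethnic-group stratum.

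The cost is SAP wording and one or two more parameters. With genotype, AUC and laboratory, 14-22 events give about 14/3 = 4.7 to 22/3 = 7.3 events per parameter, which is why the fit should be penalised and reported with its interval. The adjusted estimate is a direct effect only if nothing unmeasured, such as prior liver damage, drives both achieved AUC and VOD. The SAP should say so.

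### The genotype–busulfan PK analysis is limited to two-group tests, which leave the three GSTA1 genotypes uncoded and cannot adjust for the change of PK laboratory after 20 patients

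*Combined protocol and SAP*

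**What the plan says.** Section 14.0, under Additional Statistical Analyses, gives one sentence to this question: the link between polymorphisms and busulfan PK "will be analyzed using a t-test or non-parametric Wilcoxon rank-sum test, as appropriate". The closing phrase chooses between the two tests. It does not say which patients form the two groups, and no trend test, analysis of variance or Kruskal-Wallis test is named.

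Section 5.6 describes the loci. For GSTA1 it reports "the existence of five different alleles", and says that "two subclasses of GSTA1 can be distinguished, GSTA1A and GSTA1B with respectively two and three variants". For GSTM1 it describes "deletion of either or both genes at varying but significant frequencies in different ethnic groups". The study it cites there used the GSTM1 null genotype as the contrast, both for veno-occlusive disease and for busulfan clearance.

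The June 2006 addendum in section 14.0 records that PK for the first 20 patients was done in one laboratory, that another will be "used and technical modifications in sampling have been introduced", and that accrual therefore resumes at dose level 0. Section 10.0 still names only the original core laboratory. The analysis section does not mention laboratory.

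**The concern.** With two allele classes a patient is A/A, A/B or B/B. A t-test or rank-sum test takes two groups, so something must be done with the third, and the plan does not say what. If the effect rises with each B allele, any two-group coding gives up part of the gradient.

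The change of laboratory and sampling is a known possible source of variation in the outcome of this analysis. As named, neither test can carry a covariate, so any shift between the two periods would stay in the error term if both sets of data were used.

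At stake is a stated gap: section 5.6 says that the in-vivo link between GSTA1 genotype and busulfan PK is still to be studied. In a trial of this size, avoidable loss of precision makes a false negative more likely.

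**Working it through.** **The plan's own figure.** There is none. The documents give no sample size, alpha, power or effect size for this analysis, and no allele frequencies. Everything below is conditional on stated assumptions.

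**1. Number of genotypes.** Two GSTA1 classes give A/A, A/B and B/B. Ungrouped, five alleles give 5 × 6 / 2 = 15 genotypes.

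**2. Information lost by collapsing GSTA1.** Assume an additive effect per B allele, Hardy-Weinberg proportions, equal variances and B-allele frequency q. The loss is 1 − r², where r is the correlation between the allele count (0, 1, 2) and the two-group indicator.

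- Carrier coding (A/A versus A/B + B/B): loss = q / (2 − q). At q = 0.4: 0.4 / 1.6 = 25%.
- Homozygote coding (A/A + A/B versus B/B): loss = (1 − q) / (1 + q). At q = 0.4: 0.6 / 1.4 = 43%.

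The last two columns give the power of each collapse, Φ(2.80 × √(1 − loss) − 1.96), where the trend test has 80% power at two-sided 0.05.

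| q | Carrier loss | Homozygote loss | Carrier power | Homozygote power |
|---|---|---|---|---|
| 0.1 | 5% | 82% | 78% | 22% |
| 0.2 | 11% | 67% | 75% | 37% |
| 0.3 | 18% | 54% | 72% | 48% |
| 0.4 | 25% | 43% | 68% | 56% |
| 0.5 | 33% | 33% | 63% | 63% |

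Above q = 0.5 the two codings change places, so the better of the two never loses more than 33%. If the true effect is dominant or recessive and the grouping matches it, the loss is 0%.

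**3. Precision lost by omitting laboratory.** Assume that both sets of data are analysed together, that laboratory is unrelated to genotype, and that the shift between periods is d SD. With f = 20/N, the loss is 1 − 1 / (1 + f(1 − f)d²). N is not stated. The illustrative range runs from 40 (first 20 plus the 20 added by the addendum) to 112 (those 40 plus 72 in phase II).

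| N | f(1 − f) | d = 0.25 | d = 0.5 | d = 1 |
|---|---|---|---|---|
| 40 | 0.25 | 1.5% | 5.9% | 20% |
| 112 | 0.147 | 0.9% | 3.5% | 13% |

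A larger N shrinks this further. With 50 + 20 + 72 = 142 patients and no overlap between phases, f(1 − f) = 0.121, and the loss at 1 SD is 1 − 1/1.121 = 11%.

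**4. The same measure turned on the proposed trend test.** The squared correlation is symmetric. If the GSTA1 effect is in truth recessive (B/B versus the rest), the allele-count test loses (1 − q) / (1 + q): 54%, 43% and 33% at q = 0.3, 0.4 and 0.5, and more at lower q. If the effect is dominant, it loses q / (2 − q).

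**The case against.** A reader might infer that two-group tests are wrong for every GST locus. They are not. Although 0, 1 or 2 GSTM1 copies are possible, section 5.6 frames both its risk and its clearance findings as null versus non-null, and names confirming them as a purpose. A two-level test suits that question. This stands.

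A reader might also infer that the plan forces a collapse, that the cut-point will be chosen after seeing the data, or that the two laboratories' data are pooled. The documents are silent on all three. Pairwise comparisons, separate analyses or restriction to one laboratory would also fit the text. This stands too, but silence is not a method: pairwise tests do not use the ordering of the genotypes, and the named tests offer no adjustment if all patients are analysed together.

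No single percentage can be taken from the documents. A loss of 20–50% under both collapses, for example, holds only for q between 1/3 and 2/3 under additivity. Likewise, resuming at dose level 0 does not show that a shift was observed; the reasons given are logistics and more intensive monitoring.

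The plan does include multiple linear regression to account for other influences on metabolism. That sentence follows the GSTA1 enzymatic-activity correlation and lists no covariates. The genotype–PK sentence is in the next paragraph and names only the two tests, so the regression does not clearly cover it.

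Finally, an allele-count test is not uniformly better: a recessive effect costs it heavily (step 4 of the working). That is why it should not be imposed on GSTM1, and why the 2-df test is needed for GSTA1. The 2-df test offsets the loss only in part.

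**Conclusion.** The point holds for GSTA1 and for the laboratory change. The plan names only two-group tests where its own background implies three genotypes, and those tests cannot adjust for a documented change in how the outcome was measured. A regression answers the same question with data already collected.

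The size is conditional. The GSTA1 loss depends on additivity, Hardy-Weinberg proportions and an assumed q, and is zero if the grouping matches the true effect. The laboratory loss depends on an assumed shift and N, and is small unless the shift approaches 1 SD. It is a loss of precision, not a bias, provided that laboratory period is unrelated to genotype.

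This is a secondary analysis. Neither the MTD determination nor the one-year DFS decision depends on it. It is worth changing because the change costs almost nothing.

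**What to change.** Replace the sentence in section 14.0 with a plan along these lines:

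- **GSTA1:** regress the log-transformed PK parameter on the number of B-class alleles (0, 1 or 2), and report a 2-df test with genotype as three categories as a check on additivity.
- **GSTM1:** use null versus non-null as the regressor, stated in advance.
- **Both:** include PK laboratory and sampling period (first 20 patients versus later) as a covariate. The term absorbs both changes together and should not be read as an estimate of either.
- State how the PK data from the two periods are combined, and reconcile section 10.0, which names only the original laboratory, with the June 2006 addendum.

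The cost is SAP wording and one degree of freedom per model for period; no new patients or samples are needed. The downside is loss of power for the GSTA1 trend test if the effect is recessive, which the 2-df test only partly recovers.
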